### 3. Synopsis

The first United Nation's Millennium Development Goal is to eradicate extreme poverty and hunger. Following this objective, the European Union has been developing programs and funding research projects to assess and fight against food insecurity. WHO's European Food and Nutrition Action Plan (2015-2020) aims to reduce inequalities targeting vulnerable populations. In Portugal, the aim of the National Health Plan is to maximize health gains and to improve health in all individuals, reducing inequalities. Because of increasing autonomy that characterizes this life stage sometimes negatively influencing their eating patterns, sedentary life styles, and decreased financial resources of the families, adolescents are more likely to suffer from food insecurity. Furthermore, eating disorders are more likely to occur during adolescence and the literature has shown that both developmental tasks inherent to adolescence and pubertal changes, namely body changes, play here a key role.

Food insecurity, defined as limited or uncertain food accessibility, availability and quality, due to lack of resources, is a worldwide problem. The lack of valid epidemiological information to support decision-making constitutes a major public health challenge in Portugal. Moreover, there is a lack of management programs for adolescents targeting nutrition and well-being in order to optimize health status and reduce future co-morbidities.

Taking into account the principles above, we will conduct a longitudinal study with a mixed design, including 300 adolescents aged 12-14 years from two public schools. The intervention length is 6 months: (i) evaluation at baseline; (ii) 3 months of direct intervention; (iii) evaluation at month 3; (iv) follow-up at month 6. The intervention will include psycho-educative sessions directed to the adolescents and their parents. Furthermore, adolescents will have an access to the electronic platform and the

app developed by our team on purpose for this project, aiming to improve food security, psychological well-being, and prevent disordered eating among adolescents. The clinical endpoints will be: nutritional and physical status, well-being, and attitudes regarding eating.

Our consortium comprises a group of leading experts in different fields. The knowledge and expertise exchange among partners will assure goal attainment. We will be able to accomplish the schedule and answer to the relevant research questions addressed in the project. Our project will develop a set of psycho-educative sessions, an e-platform and an app for adolescents with the purpose of changing behaviors when needed and improve health.

### 4. Background and rationale

Nutrition status is a key indicator of poverty, hunger, poor health, inadequate education and social condition (1). The first United Nations' Millennium Development Goal is to eradicate extreme poverty and hunger. According to the European Parliament, the estimated losses linked to health inequalities had cost around 1.4% of GDP within the European Union in 2011 (2-4). Following this objective, the European Union has been developing programs and funding research projects to assess and fight against food insecurity. The new WHO's European Food and Nutrition Action Plan (2015-2020) established the reduction of inequalities in access to healthy food as a priority goal for food and nutrition policies in the European context (5). In Portugal, the aim of the National Health Plan (6) is to maximize health gains by involving all social partners at national, regional and local levels in the promotion of healthy policies and to improve health in all individuals, reducing inequalities. Moreover, the Portuguese Program for the Promotion of Healthy Eating (PNPAS), also considers the reduction of inequalities in diet as a one of its main challenges (7).

Food insecurity concept includes uncertainty or worry about food, inadequate quality of food, inadequate quantity of food, food acquired through socially unacceptable means, and lack of consistent access to adequate food (8). Rates of food insecurity have been rising worldwide (8). In fact, while the United States is one of the wealthiest nations in the world with a rich and abundant supply of food and resources, 14.3% of U.S. households were food insecure at some point in time during 2013 (9).

A study in Portuguese primary care centers attendees in 2012 showed that 49.0% were food insecure (10). Research has shown that young children are often protected from hunger even in households that have very low food security; however, adolescents may be more vulnerable (11). In adolescence, food insecurity showed to be associated

with poor well-being and psychosocial functioning (12), risk of suicidal behaviors (13) and overweight status (14, 15). Because of decreased financial resources of the families, increasing sedentary life styles and poor eating habits, adolescents are more likely to experiment adverse health conditions. Eating disorders (e.g., anorexia, binge eating, and eating disorders without other specification) and obesity are more likely to occur during adolescence (16). Portugal has one of the highest overweight prevalence rates in Europe (17). Several studies have pointed a paradoxical association between household food insecurity and overweight status in children (14, 15).

In the project *E-therapeutic intervention program for obese adolescents and their family*, funded by the Foundation for Science and Technology (PTDC / DTP-PIC / 0769/2012) and coordinated by [name], an e-platform was developed aimed to support and to manage adolescent obesity (Next.Step). The preliminary results showed that the platform is effective in promoting healthy behaviors, suggesting the relevance of technological tools as catalysts of behavioral change in Portuguese adolescents. So, based on our previous knowledge on e-intervention tools for adolescents, we intend to design a new platform and an app to promote healthy life styles, and promote food security as well as prevent disordered eating including obesity among adolescents.

Research on the association between food insecurity and well being in adolescence is scarce. Little is known about the effectiveness of interventions to reduce food security by promoting healthy life styles and psychological well-being and preventing disordered eating. Based on the literature search, we hypothesized that: (i) At 3 and 6 months adolescents will show lower indicators of food insecurity compared to the indicators of food insecurity at baseline; (ii) psychological well-being variables mediate the relationship between food insecurity and disordered eating.

### 5. Objective and endpoints

### 5.1. General objectives

- To improve food security, psychological well-being and eating attitudes among adolescents.
- To test the effectiveness and the determinants associated with the success of the intervention (short and long-term).

### 5.2. Primary objectives

- To improve nutritional status and eating habits in this adolescent population.
- To study the evolution of the variable "Food insecurity" (T0-T1-T2) in this population.

### 5.3. Secondary objectives

To improve several clinical endpoints, such as:

- Psychological well-being
- Physical activity habits

### 5.4. Primary endpoints

- Changes in indicators of nutritional habits (preference towards healthy foods, perceived benefits of healthy eating, fast food intake, family meal frequency, having breakfast on a regular basis; attitudes regarding eating) among these adolescents at 3 and 6 months.
- Changes in food insecurity in households (based on the Food Insecurity Questionnaire) at 3 and 6 months;

### 5.5. Secondary endpoints

- Changes in indicators of nutritional status (BMI, waist circumference and fat mass) among this adolescent population at 3 and 6 months.
- Changes in the psychological well-being, physical activity and body image at 3 and 6 months.

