### 7. Study population

### 7.1. Overview

This study will include adolescents aged between 12 and 13 years who are attending school. This age range has been consistently identified as a critical period for prevention because it is a crucial period of adolescents' physical and cognitive development. The characteristics of this developmental period (e.g. the emergence of formal thought, body changes and evolving social relationships) will be key ingredients to potentiate the discussion and the integration of healthy lifestyle messages.

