### 7.2. Inclusion criteria

To be eligible for this randomized controlled study, adolescents must fulfill the following inclusion criteria: age between 12 and 13 years; capable of computer use.

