### 8.3. Task 3: Perform the study

In Task 3, we will conduct a longitudinal study with a mixed design. The intervention will last 3 months. Adolescents will be followed over 6 months.

Baseline, 3-month and 6-month evaluations will be conducted to collect anthropometric data (BMI, waist circumference and fat mass) and to apply validated questionnaires to adolescents and parents. In order to evaluate the economic determinant of food security, parents will answer to the food security questionnaire. Adolescents will answer to:

- Socio-demographic questionnaire;
- Physical and eating health questionnaire, adapted from Health Behaviour in Schoolaged Children (2010) and from Project Eat (18) (to evaluate the contextual determinants of food security);
- Nutrition questionnaire (NUT-Q, Raich et al., 2008);
- Eating Attitudes Test-26 (EAT-26; Garner & Garfinkel, 1979);
- Contour Drawing Rating Scale (CDRS; Thompson & Gray, 1995);
- EADS-21 (Lovibond & Lovibond; validated by Pais-Ribeiro, Honrado, & Leal 2004)
- Adolescent anthropometric data (weight, height, BMI, waist circumference and fat mass).

In each classroom, an identification of the group leader will take place with the purpose of facilitating adherence.

In both, platform and app, adolescents can choose to use a nick name to protect their identity. The adolescents will be presented to life situations and simulated cases and will be stimulated to present specific strategies directed to the promotion of food security and healthy lifestyles based on the cases presented. Adolescents will be motivated to comment the suggested strategies among them.

Culinary tips including healthy and low cost meals and physical activity tips will also be included. Adolescents will be stimulated to experiment these contents and comment on them.

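### Change in BMI, waist and fat mass is read as programme impact with no growth reference and no described control arm, so expected growth is confounded with the effect

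*Protocol*

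**What the plan says.** Section 5.5 of the protocol defines the nutritional-status endpoint as "Changes in indicators of nutritional status (BMI, waist circumference and fat mass) among this adolescent population at 3 and 6 months". Section 8.3 lists what is recorded: "Adolescent anthropometric data (weight, height, BMI, waist circumference and fat mass". Neither place, nor any other, mentions a z-score, percentile, growth reference, waist-to-height ratio, or adjustment for age, sex or puberty.

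Section 7.2 admits pupils by "age between 12 and 13 years; capable of computer use"; the synopsis instead describes a study "including 300 adolescents aged 12-14 years from two public schools". Section 7.1 justifies the age range because "it is a crucial period of adolescents' physical and cognitive development" and gives "body changes and evolving social relationships" among its features.

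Section 11.2 assigns Study 5 a repeated-measures factorial ANOVA per variable, with Bonferroni-adjusted comparisons at .05. Section 8.4 says Study 5 judges the intervention's impact from change over the three visits, and it names anthropometric data among the outcomes. The one directional hypothesis on change, in section 4, is also a comparison with baseline: "At 3 and 6 months adolescents will show lower indicators of food insecurity compared to the indicators of food insecurity at baseline".

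Sections 3, 6 and 8.3 describe the sessions, platform and app as given to all participants. Section 7.2 calls the study randomised and controlled, but no arms, allocation or control condition appear anywhere.

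**The concern.** BMI depends on age in early adolescence, and waist in centimetres grows with body size, as does fat mass if it is recorded in kilograms. Over six months the expected change with no programme is therefore not zero. A one-sample comparison with baseline tests whether mean change is zero, so it tests growth and programme together. Including sex as a factor would not help, because the time effect would still contain growth.

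Two errors are possible. An ineffective programme could show a significant change, or a useful effect could be offset by growth and missed. These are secondary endpoints, but section 5.2 makes improving nutritional status a primary objective, so the result will carry weight.

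**Working it through.** **What can be reproduced.** Section 11.1 states 300 pupils, six classes from each of two schools, which gives 300/12 = 25 per class. The protocol gives no power, effect size, SD or dropout, so there is no further figure to reproduce.

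**Inputs from the protocol.** n = 300; three visits, hence three pairwise comparisons; Bonferroni at .05, so 0.05/3 = 0.0167 per pair, two-sided critical value 2.394.

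**Assumed inputs.** Mean six-month BMI drift from growth d = 0.1 to 0.4 kg/m²; SD of individual six-month change s = 0.8 to 1.5 kg/m². The protocol gives neither.

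**Formula.** With no programme effect, L = d / (s/√n), and the chance of a significant T0-T2 change is Φ(L − 2.394) + Φ(−L − 2.394).

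**Example.** d = 0.2, s = 1.0: s/√300 = 0.0577; L = 0.2/0.0577 = 3.46; Φ(3.46 − 2.394) = Φ(1.07) = 0.86.

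| Drift (kg/m²) | SD 0.8 | SD 1.0 | SD 1.5 |
|---|---|---|---|
| 0 | 1.7% | 1.7% | 1.7% |
| 0.1 | 41% | 25% | 11% |
| 0.2 | 97% | 86% | 47% |
| 0.3 | about 100% | 99.7% | 86% |
| 0.4 | about 100% | about 100% | 99% |

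The drift found with 80% probability is 0.15 kg/m² at SD 0.8 and 0.28 kg/m² at SD 1.5.

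**Fewer completers.** With 200 pupils and SD 1.0, the chance is 16% at a drift of 0.1 and 67% at 0.2.

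**Clustering by class.** Assume an intraclass correlation of 0.05 in change. The design effect is 1 + 24 × 0.05 = 2.2 and the effective n is 300/2.2 = 136. For a test that allows for class, with SD 1.0, the chances are 11%, 48%, 87% and 99% at drifts of 0.1, 0.2, 0.3 and 0.4. The lowest cell (drift 0.1, SD 1.5) falls to 5%.

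**Masking.** If the programme lowered BMI by 0.2 kg/m² while growth raised it by 0.2, the expected observed change is 0.2 − 0.2 = 0, and the effect would be found only at the nominal 1.7%.

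**After standardising.** For a score whose expected change under normal growth is zero, L = 0 and the chance returns to 1.7% per pair. This holds only as far as the chosen reference fits these pupils.

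No comparable figures are given for waist or fat mass. The argument there is about direction, not size.

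**The case against.** **The protocol never says that raw values will be analysed.** Height and weight are collected, and a separate analysis plan, not shown here, could derive z-scores. That is true. But the protocol is where the endpoint is defined, and it names only unstandardised measures. A z-score would change that definition rather than fill in a detail.

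**There may be a control group.** Section 7.2 says randomised and controlled, and a factorial ANOVA can carry a between-subject factor. If randomised arms existed, growth would largely cancel between them. A reader therefore cannot take the absence of a control as settled fact; what can be said is that none is described and that sections 3, 6 and 8.3 read as a single group. The passages must be reconciled. Comparing food-insecure pupils with others, which Study 5 suggests, would not supply an untreated comparison.

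**The size is assumed.** This stands. A reader might infer that the analysis is bound to show a significant worsening. The documents do not support that: at a drift of 0.15 and SD 1.5, L = 0.15/(1.5/√300) = 1.73, and at SD 1.0 with an effective n of 136, L = 1.75. Both are below 2.394.

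**Direction.** A reader might also infer that the plan counts lower BMI as better. It does not; sections 5.2 and 5.5 speak only of improvement and change. What remains is that no direction of improvement is defined, and a mean change cannot separate pupils for whom a rise is favourable from those for whom it is not.

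**Conclusion.** The point holds as a confounding problem in how the endpoint is defined and read. With pupils of 12-13 (or 12-14), no growth reference and no described control arm, change from T0 to T2 mixes expected growth with any programme effect. That conclusion needs no assumed figure and is the same for either age range.

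The size does rest on assumptions: about 11% to nearly 100% chance of a significant BMI change with no programme effect, for 300 independent completers and the stated ranges of drift and SD, against 1.7% nominal. Dropout, or a test that allows for class, lowers these figures. The supported wording is that growth could produce or mask a significant change, not that the nutritional-status conclusion will be wrong. As the measures are secondary endpoints, this is a change that should be made rather than one that invalidates the study.

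**What to change.** - In sections 5.5 and 11.2, analyse BMI as a BMI-for-age-and-sex z-score against a named growth reference, using age at each visit. Report the share of pupils who are under-, normal- and overweight at each visit.
- Report waist as waist-to-height ratio and, if fat mass is measured in kilograms, scale it to height. State the unit of fat mass. State that these two scalings remove growth in height only, not all pubertal change.
- In section 8.4 (Study 5), state that standardising does not remove seasonal, secular or regression-to-the-mean effects, and do not call uncontrolled change in these measures an intervention effect. Section 10 places baseline in September and the last visit in March, so season is a live alternative explanation.
- Reconcile section 7.2 with sections 3, 6 and 8.3 on whether a control arm exists, and the two age ranges with each other.

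The cost is derivation work. Weight and height are already collected, age is an eligibility criterion and sex is already an analysis variable in Study 2. Date of birth must be recorded so that age at each visit is exact; the content of the socio-demographic questionnaire is not shown, so this should be confirmed. No extra visit or participant is needed.

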### 6. Project design

We will perform an interventional study on food security, psychological wellbeing and healthy eating using a sample of Portuguese adolescents. An e-platform, an app and specific psycho-educative sessions will be developed to support this study.

About 300 community adolescents from two schools will be invited to participate in a study. The intervention length is 6 months: (i) three months of direct intervention; (ii) evaluation at baseline, month 3, and follow-up at month 6.

- (i) Evaluation at baseline (T0)
- Application of validated questionnaires;
- Collection of anthropometric measures;
- Introduction to the use of the platform and the app;
- One psycho-educative session on healthy life styles for adolescents and another for parents.
- (ii) Evaluation at 3-months (T1)
- Application of validated questionnaires;
- Collection of anthropometric measures;
- One psycho-educative session for adolescents and another for parents. The psycho-educative sessions will focus on the discussion of the strategies to improve health lifestyles which have meanwhile been developed in the platform and the app some of them by the adolescents themselves.
- (iii) Evaluation at 6-months (T2)
- Application of validated questionnaires; collection of anthropometric measures.

The interactive e-platform and app will allow for the delivery and collection of information; discussion of nutritional and physical activities; share of solutions and strategies; favor cohesion among adolescents; promotion of behavior change. Psycho-

educative sessions will play an important role for discussing potential strategies to promote change.

The same validated questionnaires will be applied at T0, T1 and T2. Our team will apply robust statistical methods. The trial will follow the principles of best clinical practices, all adolescents and their parents will sign an informed consent and all procedures will be submitted to an Ethics Committee and to *Ministério da Educação* – *Monitorização dos inquéritos em meio escolar*.

Our aim is to assess the short and long-term change in clinical endpoints. This study has a high likelihood of success attending to the vast expertise of the team members involved in handling large studies, psychosocial variables assessment, interventions with adolescents, development of psycho-educative sessions, and management of group dynamics.

To accomplish our aims, this project comprises the following tasks:

Task 1 – Development and design of the interactive platform and the app;

Task 2 – Development of the psycho-educative sessions for adolescents and parents;

Task 3 – Perform the longitudinal study with a mixed design;

Task 4 – Evaluation of the impact of the intervention and development of the final report; production of scientific papers and dissemination of the results.

### 7. Study population

### 7.1. Overview

This study will include adolescents aged between 12 and 13 years who are attending school. This age range has been consistently identified as a critical period for prevention because it is a crucial period of adolescents' physical and cognitive development. The characteristics of this developmental period (e.g. the emergence of formal thought, body changes and evolving social relationships) will be key ingredients to potentiate the discussion and the integration of healthy lifestyle messages.

### 7.2. Inclusion criteria

To be eligible for this randomized controlled study, adolescents must fulfill the following inclusion criteria: age between 12 and 13 years; capable of computer use.

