### 10. Project schedule

This project will start in June 2015, although some of the materials have already started to be developed. Baseline evaluation is planned for September 2015. The planned data for completion the follow-up evaluation is March 2016.

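### Section 7.2 labels the study randomized and controlled, but no control or allocation is described, so change from baseline cannot be attributed to the programme as Sections 5.1 and 8.4 intend

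*Protocol*

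**What the plan says.** The label appears once, in Section 7.2: "To be eligible for this randomized controlled study, adolescents must fulfill the following inclusion criteria".

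The other design text runs differently:

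- **Synopsis (Section 3):** "we will conduct a longitudinal study with a mixed design, including 300 adolescents aged 12-14 years from two public schools". The term *mixed design* recurs in Sections 6 and 8 and is never defined.
- **Hypothesis (Section 4):** "At 3 and 6 months adolescents will show lower indicators of food insecurity compared to the indicators of food insecurity at baseline".
- **Objective (Section 5.1):** "To test the effectiveness and the determinants associated with the success of the intervention (short and long-term". Section 5.2 adds a primary objective of following food insecurity across T0, T1 and T2.
- **Endpoints (Sections 5.4 and 5.5):** all are changes at 3 and 6 months. None is a difference between groups.
- **Design (Section 6):** "We will perform an interventional study on food security, psychological wellbeing and healthy eating using a sample of Portuguese adolescents", and "About 300 community adolescents from two schools will be invited to participate in a study". Sessions are placed at T0 and T1 and the platform and app are introduced at T0, with no untreated subset mentioned.
- **Schedule (Section 10):** "Baseline evaluation is planned for September 2015", with follow-up to be completed in March 2016.
- **Analysis (Sections 8.4 and 11.2):** Study 5 is to evaluate the effect of the intervention over time, in particular among adolescents classed as food insecure in Study 1. It uses repeated-measures factorial ANOVA with Bonferroni-adjusted comparisons at 0.05. No treatment factor is named.

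**The concern.** A reader of Section 7.2 alone would expect a concurrent, randomly allocated comparison group. The rest of the protocol gives none, so the contrast behind the effectiveness claim is each adolescent against his or her own baseline. Between September and March the season changes, the adolescents grow by six months (at an age that Section 7.1 itself describes as crucial for physical and cognitive development), and they complete the same questionnaires three times. Any of these could shift eating habits, anthropometry, body image or well-being without the programme, in either direction.

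Study 5 adds a second problem. It concentrates on adolescents selected for food insecurity at baseline. A group selected for extreme values on an imperfectly stable measure tends to look better at the next measurement whatever is done in between.

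At stake is what the trial may conclude, and whether the ethics committee, schools and families are told the right kind of study.

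**Working it through.** **Step 1. Is there any support for the label?** A randomized controlled design needs a comparator, a unit of allocation and a between-group contrast. The synopsis, Sections 4, 5, 6 and 8.3, Study 5 in 8.4, and 11.1 and 11.2 were read for each. None is present. Two terms could hint at a second group. *Mixed design* may mean between-within, or quantitative plus qualitative. *Factorial* implies a second factor, but food-insecurity status or sex would serve. Neither term defines a control arm.

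**Step 2. Sample size.** Section 11.1 gives 300 adolescents in 6 classes per school: 2 × 6 = 12 classes, and 300/12 = 25 per class. No power inputs are stated, so the 300 cannot be reproduced from a formula.

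**Step 3. False attribution under drift (illustration).** Assumed: background drift d of 0.10, 0.15 or 0.20 SD of the change score, no programme effect, 300 complete cases, pupils treated as independent. For a two-sided paired t test with 299 df, the noncentrality is d√300. The critical value is 1.968 at 0.05, and 2.408 at 0.05/3 = 0.0167 for the three visit pairs.

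| Drift (SD of change) | d√300 | Significant, unadjusted | Significant, Bonferroni for 3 pairs |
|---|---|---|---|
| 0.10 | 1.73 | 41% | 25% |
| 0.15 | 2.60 | 74% | 58% |
| 0.20 | 3.46 | 93% | 85% |

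Without drift the rates are 5% and 1.7%. Bonferroni controls chance findings across comparisons. It does not remove bias.

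**Step 4. Regression to the mean in the food-insecure subgroup (illustration).** If the worst share p is selected on a normally distributed baseline score with between-visit correlation r, the expected apparent improvement is [φ(z)/p](1 − r) SD, where z is the upper-p normal quantile. For a range of p, take the two background prevalences in Section 4, 14.3% and 49.0%; r of 0.5 to 0.8 is assumed.

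- p = 0.143: φ(z)/p = 1.579, giving 1.579 × 0.5 = 0.79 SD down to 1.579 × 0.2 = 0.32 SD.
- p = 0.49: φ(z)/p = 0.814, giving 0.814 × 0.5 = 0.41 SD down to 0.814 × 0.2 = 0.16 SD.

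The range is therefore 0.16 to 0.79 SD with no programme effect. Study 1 identifies the group by cluster analysis, so a simple cut-off is only a stand-in.

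**Step 5. What the same 12 classes could detect if randomized 6 against 6.** Detectable difference at 80% power, two-sided 0.05, 10 df: (2.228 + 0.879) × √[2(1 − r²)(1 + 24 × ICC)/150], where r is now the correlation with baseline used for adjustment.

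| Assumed ICC | Design effect | No baseline adjustment | r = 0.5 | r = 0.7 |
|---|---|---|---|---|
| 0.02 | 1.48 | 0.44 SD | 0.38 SD | 0.31 SD |
| 0.05 | 2.20 | 0.53 SD | 0.46 SD | 0.38 SD |

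The range is about 0.31 to 0.46 SD with adjustment and 0.44 to 0.53 SD without. Randomizing within school would use one more degree of freedom, with trivial effect.

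**The case against.** The strongest reply is that a single cohort can deliver much of what is planned. Section 5.2 asks how food insecurity evolves, and Section 5.4 defines the endpoints as changes at 3 and 6 months. That stands. A reader might infer that the study's objectives cannot be met at all, but the documents do not support that: description of change is an objective and is achievable. What fails is attribution to the programme.

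Three other strong readings are also tempting.

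- *The protocol states a single group in which every adolescent receives everything.* It does not. This is inferred from the hypothesis, the endpoints and the absence of any comparator, and *mixed design* leaves some doubt.
- *There is no between-subject factor for the factorial ANOVA.* Food-insecurity status is a candidate from Study 5, and sex is a named moderator in Study 2. Only a treatment factor is absent, and listing the other factors may belong in an analysis plan that is not shown.
- *A full school year of growth is confounded with the programme.* September to March is six months.

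The drift, correlation and ICC values have no source in the protocol, and 300 complete cases is favourable given that about 300 are to be invited. The percentages therefore show how the design behaves and do not estimate actual bias. The contradiction and the limit on attribution do not depend on them. Nor can an analysis plan supply a control group that the design lacks.

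**Conclusion.** The point holds. Section 7.2 is inconsistent with the rest of the protocol, and the effectiveness and impact claims in 5.1 and 8.4 rest, as written, on an uncontrolled before-after comparison. That conclusion comes from the text alone.

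Its possible size depends on assumptions. With modest drift, a programme that does nothing would be declared to produce change in roughly a quarter to five-sixths of studies under the planned adjustment (25% to 85%), and more often without it. In the food-insecure subgroup, regression to the mean could add an apparent gain of 0.16 to 0.79 SD. If a control arm was in fact intended, the label may be right, but then the whole description of that arm is missing.

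**What to change.** Reconcile Section 7.2 with Sections 4 to 6, 8.3, 8.4 and 11.2. This should be settled before the baseline assessment.

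- **If there is no control arm:** delete the words randomized and controlled from 7.2. Restate 5.1 and 8.4, including Study 5, as describing change from baseline after the programme. State that season, growth and retesting cannot be separated from it, and that the food-insecure subgroup is subject to regression to the mean. Define *mixed design* and *factorial* to match. The cost is wording only.
- **If a control arm is intended:** state the control condition, the unit of randomization and the allocation. The unit should be classes within school; allocating the two schools would leave one cluster per arm and confound school with programme. Make a group-by-time contrast that allows for class clustering the main analysis. This is a substantive amendment and needs ethics approval.

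A delayed start, with three of the six classes in each school starting after T2, is one optional way to obtain a control with the same pupils and assessment visits. It has real costs. Adolescents share strategies through the platform and app, so contamination between classes is likely. Half the classes would receive the programme after the planned March 2016 completion. Power would be limited to the detectable differences in the working.
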